### **Study Design**

#### **Description of Study**

This Phase Ib/II, open-label, multicenter, non-randomized, dose-escalation study will evaluate the safety, efficacy, and pharmacokinetics of G+Pola+Len in patients with R/R FL *and R + Pola + Len in patients with R/R DLBCL*. The study will include an initial dose-escalation phase, followed by an expansion phase, during which polatuzumab vedotin and lenalidomide will be given at their RP2Ds.

All patients will be closely monitored for adverse events throughout the study and for at least 90 days after the last dose of study treatment. Adverse events will be graded according to the National Cancer Institute Common Terminology Criteria for Adverse Events (NCI CTCAE), Version 4.0. An Internal Monitoring Committee (IMC) will be established to monitor patient safety throughout the study.

To characterize the PK properties of obinutuzumab, *rituximab*, polatuzumab vedotin, and lenalidomide, blood samples will be obtained at various timepoints before and during study treatment administration.

Response will be determined by the IRC and the investigator using the Lugano 2014 criteria. The primary efficacy endpoint will be based on IRC assessment of response.

### **Number of Patients**

Approximately 110–128 patients are expected to be enrolled in this study, at approximately 20–25 investigative sites worldwide.

### **Target Population**

#### Inclusion Criteria

Patients must meet the following criteria for study entry:

- Signed Informed Consent Form
- Age  $\geq$  18 years
- Eastern Cooperative Oncology Group Performance Status of 0, 1, or 2
- *For G + Pola + Len treatment group:* R/R FL after treatment with at least one prior chemoimmunotherapy regimen that included an anti-CD20 monoclonal antibody and for which no other more appropriate treatment option exists as determined by the investigator
- *For R + Pola + Len treatment group:* R/R DLBCL after treatment with at least one prior chemoimmunotherapy regimen that included an anti-CD20 monoclonal antibody in patients who are not eligible for autologous stem-cell transplantation or who have experienced disease progression following treatment with high-dose chemotherapy plus autologous stem-cell transplantation
- Histologically documented CD20-positive B-cell lymphoma as determined by the local laboratory
- Fluorodeoxyglucose-avid lymphoma (i.e., PET-positive lymphoma)
- At least one bi-dimensionally measurable lesion ( $>$  1.5 cm in its largest dimension by CT scan or magnetic resonance imaging)
- Availability of a representative tumor specimen and the corresponding pathology report for retrospective central confirmation of the diagnosis of FL or DLBCL

If the archival tissue is unavailable or unacceptable, a pretreatment core-needle, excisional, or incisional tumor biopsy is required. Cytological or fine-needle aspiration samples are not acceptable.

*If the patient received anti-lymphoma treatment between the time of the most recent available biopsy and initiation of study treatment, a repeat core-needle biopsy is strongly recommended.*

- Agreement to abstain from donating blood during the treatment period (including periods of treatment interruption) and for 28 days after the last dose of study treatment
- Agreement not to share study medication with another person
- Agreement to comply with all local requirements of the lenalidomide risk minimization plan

In every country where lenalidomide has been approved, a risk minimization plan, which includes a pregnancy prevention program, is in place. The risk minimization plan should be followed by patients using lenalidomide.

***US sites only:** Per standard Revlimid REMS™ requirements, all physicians who prescribe lenalidomide for research subjects enrolled into this study, and all research subjects enrolled into this study, must be registered in and must comply with all requirements of the Revlimid REMS™ program.*

***For Ex-US sites only:** Subjects will be counseled on pregnancy prevention prior to medication being dispensed to ensure that the subject has complied with all requirements including use of birth control and pregnancy testing and that the subject understands the risks associated with lenalidomide. This step will be*

*documented with a completed Education and Counseling Guidance Document (refer to Lenalidomide Pregnancy Prevention Risk Management Plans), and no drug will be dispensed until this step occurs. Counseling includes verification with the subject that required pregnancy testing was performed and results were negative. A Lenalidomide Information Sheet (refer to Lenalidomide Pregnancy Prevention Risk Management Plans) will be supplied with each medication dispense. All requirements must be followed by each site as noted within the Lenalidomide Pregnancy Prevention Risk Management Plans.*

In addition, because lenalidomide will be administered in combination with obinutuzumab, *rituximab*, and polatuzumab vedotin, patients must comply with contraceptive measures designed to ensure safe administration of all study treatments as outlined below.

- For women of childbearing potential: agreement to remain abstinent (refrain from heterosexual intercourse) or use two adequate methods of contraception, including at least one method with a failure rate of <1% per year, for at least 12 months after the last dose of polatuzumab vedotin, 28 days after the last dose of lenalidomide, 12 months after the last dose of rituximab, and 28 days prior to Day 1 of Cycle 1, during the treatment period (including periods of treatment interruption), and for at least 18 months after the last dose of obinutuzumab.

A woman is considered to be of childbearing potential if she is postmenarcheal, has not reached a postmenopausal state ( $\geq 24$  continuous months of amenorrhea with no identified cause other than menopause), and has not undergone surgical sterilization (removal of ovaries and/or uterus).

Examples of contraceptive methods with a failure rate of <1% per year include bilateral tubal ligation, male sterilization, established, proper use of progestogen-only hormonal contraceptives that inhibit ovulation, hormone-releasing intrauterine devices, and copper intrauterine devices. Combined oral contraceptives are not recommended because of the increased risk of venous and arterial thromboembolism (TE) in patients taking lenalidomide.

Barrier methods may be used as the second contraceptive method but must always be supplemented with the use of a spermicide.

- The reliability of sexual abstinence should be evaluated in relation to the duration of the clinical trial and the preferred and usual lifestyle of the patient. Periodic abstinence (e.g., calendar, ovulation, symptothermal, or postovulation methods) and withdrawal are not acceptable methods of contraception. For men: agreement to remain abstinent (refrain from heterosexual intercourse) or use contraceptive measures and agreement to refrain from donating sperm, as defined below:

With female partners of childbearing potential, men must remain abstinent or use a condom plus an additional contraceptive method that together result in a failure rate of <1% per year during the treatment period and for at least 5 months after the last dose of polatuzumab vedotin, 28 days after the last dose of lenalidomide, and 3 months after the last dose of obinutuzumab or rituximab. Men must refrain from donating sperm during this same period.

With pregnant female partners, men must remain abstinent or use a condom during the treatment period and for at least 5 months after the last dose of polatuzumab vedotin, 28 days after the last dose of lenalidomide, and 3 months after the last dose of obinutuzumab or rituximab to avoid exposing the embryo.

The reliability of sexual abstinence should be evaluated in relation to the duration of the clinical trial and the preferred and usual lifestyle of the patient. Periodic abstinence (e.g., calendar, ovulation, symptothermal, or postovulation methods) and withdrawal are not acceptable methods of contraception.

## Exclusion Criteria

Patients who meet any of the following criteria will be excluded from study entry:

- *Grade 3b follicular lymphoma*
- *History of transformation of indolent disease to DLBCL*
- Known CD20-negative status at relapse or progression
- Central nervous system lymphoma or leptomeningeal infiltration
- Prior allogeneic stem-cell transplantation (SCT)
- Completion of autologous SCT within 100 days prior to Day 1 of Cycle 1
- History of resistance to lenalidomide or response duration of < 1 year (for patients who had a response to a prior lenalidomide-containing regimen)
- Prior standard or investigational anti-cancer therapy as specified below:
  - Lenalidomide, fludarabine, or alemtuzumab within 12 months prior to Day 1 of Cycle 1
  - Radioimmunoconjugate within 12 weeks prior to Day 1 of Cycle 1
  - Monoclonal antibody or antibody-drug conjugate therapy within 5 half-lives or 4 weeks prior to Day 1 of Cycle 1, *whichever is longer*
  - Radiotherapy, chemotherapy, hormonal therapy, or targeted small-molecule therapy within 2 weeks prior to Day 1 of Cycle 1
- Clinically significant toxicity (other than alopecia) from prior therapy that has not resolved to Grade  $\leq 2$  (per NCI CTCAE, Version 4.0) prior to Day 1 of Cycle 1
- Treatment with systemic immunosuppressive medications, including, but not limited to, prednisone, azathioprine, methotrexate, thalidomide, and anti-tumor necrosis factor agents within 2 weeks prior to Day 1 of Cycle 1
  - Treatment with inhaled corticosteroids and mineralocorticoids is permitted.
  - If corticosteroid treatment is urgently required for lymphoma symptom control prior to the start of study treatment, up to 100 mg/day of prednisone or equivalent can be given for a maximum of 5 days, but all tumor assessments must be completed prior to initiation of corticosteroid treatment.
- History of severe allergic or anaphylactic reaction to humanized or murine monoclonal antibodies
- Known sensitivity or allergy to murine products or any component of obinutuzumab, *rituximab*, polatuzumab vedotin, or lenalidomide formulations
- History of erythema multiforme, Grade  $\geq 3$  rash, or desquamation (blistering) following prior treatment with immunomodulatory derivatives such as thalidomide and lenalidomide
- Active bacterial, viral, fungal, or other infection
  - Caution should be exercised when considering the use of obinutuzumab *and rituximab* in patients with a history of recurring or chronic infections.
- Positive for hepatitis B surface antigen, total hepatitis B core antibody, or hepatitis C virus antibody at screening
- Known history of HIV positive status
  - For patients with unknown HIV status, HIV testing will be performed at screening if required by local regulations.
- History of progressive multifocal leukoencephalopathy
- Vaccination with a live virus vaccine within 28 days prior to Day 1 of Cycle 1
- History of other malignancy that could affect compliance with the protocol or interpretation of results, with the exception of the following:
  - Curatively treated carcinoma in situ of the cervix; good-prognosis ductal carcinoma in situ of the breast; basal- or squamous-cell skin cancer; Stage I melanoma; or low-grade, early-stage localized prostate cancer

Any previously treated malignancy that has been in remission without treatment for  $\geq 2$  years prior to enrollment

- Contraindication to treatment for TE prophylaxis
- Grade  $\geq 2$  neuropathy
- Evidence of any significant, uncontrolled concomitant disease that could affect compliance with the protocol or interpretation of results, including significant cardiovascular disease (such as New York Heart Association Class III or intravenous (IV) cardiac disease, myocardial infarction within the previous 6 months, unstable arrhythmia, or unstable angina) or significant pulmonary disease (such as obstructive pulmonary disease or history of bronchospasm)
- Major surgical procedure other than for diagnosis within 28 days prior to Day 1 of Cycle 1 or anticipation of a major surgical procedure during the course of the study
- Inadequate hematologic function (unless due to underlying lymphoma), defined as follows:
  - Hemoglobin  $< 9$  g/dL
  - ANC  $< 1.5 \times 10^9/L$
  - Platelet count  $< 75 \times 10^9/L$
- Any of the following abnormal laboratory values (unless due to underlying lymphoma):
  - Calculated creatinine clearance  $< 50$  mL/min (using the Cockcroft-Gault formula)
  - AST or ALT  $> 2.5 \times$  upper limit of normal (ULN)
  - Serum total bilirubin  $> 1.5 \times$  ULN (or  $> 3 \times$  ULN for patients with Gilbert syndrome)
  - INR or PT  $> 1.5 \times$  ULN in the absence of therapeutic anticoagulation
  - PTT or aPTT  $> 1.5 \times$  ULN in the absence of a lupus anticoagulant
- Pregnant or lactating, or intending to become pregnant during the study
  - Women of childbearing potential must have two negative serum pregnancy test results (minimum sensitivity, 25 mIU/mL) prior to initiating therapy: at 10–14 days prior to Day 1 of Cycle 1 and within 24 hours prior to Day 1 of Cycle 1.
- Life expectancy  $< 3$  months
- Unable to comply with the study protocol, in the investigator's judgment

### **End of Study**

The end of this study is defined as the time when both of the following criteria are met:

- All enrolled patients with FL have *been followed for at least 90 days after they have completed or discontinued study treatment (including induction treatment and maintenance treatment as applicable).*
- All enrolled patients with DLBCL have been followed for at least 1 year after they have completed or discontinued study treatment (including induction treatment and consolidation treatment as applicable).

### **Length of Study**

The total length of the study, from screening of the first patient to the end of the study, is expected to be approximately 5 years.

### **Investigational Medicinal Products**

The investigational medicinal products for this study are obinutuzumab, *rituximab*, polatuzumab vedotin, and lenalidomide.

### **Dosing Schedule for Patients with Relapsed or Refractory Follicular Lymphoma**

#### **Obinutuzumab**

##### Dose-Escalation Phase, Induction

Patients will receive obinutuzumab 1000 mg IV on Days 1, 8, and 15 of Cycle 1 and on Day 1 of each subsequent 28-day cycle for up to a total of 6 cycles.

#### Expansion Phase, Induction

Patients will receive obinutuzumab 1000 mg IV on Days 1, 8, and 15 of Cycle 1 and on Day 1 of each subsequent 28-day cycle for up to a total of 6 cycles.

#### Post-Induction (Maintenance Treatment)

Patients will receive obinutuzumab 1000 mg IV on Day 1 of every other month (i.e., every 2 months), starting with Month 1 (i.e., Months 1, 3, 5, 7, 9, 11, 13, 15, 17, 19, 21, and 23) for a maximum of 24 months

### **Polatuzumab Vedotin**

#### Dose-Escalation Phase, Induction

Patients will receive polatuzumab vedotin 1.4 or 1.8 mg/kg IV on Day 1 of each 28-day cycle for up to 6 cycles.

#### Expansion Phase, Induction

Patients will receive polatuzumab vedotin RP2D (mg) by mouth (PO) on Day 1 of each 28-day cycle for up to 6 cycles.

#### Post-Induction (Maintenance)

No polatuzumab vedotin will be administered.

### **Lenalidomide**

#### Dose-Escalation Phase, Induction

Patients will receive lenalidomide 10, 15, or 20 mg PO once daily on Days 1–21 of each 28-day cycle for up to 6 cycles.

#### Expansion Phase, Induction

Patients will receive lenalidomide RP2D (mg) PO once daily on Days 1–21 of each 28-day cycle for up to 6 cycles.

#### Post-Induction

Patients will receive lenalidomide 10 mg PO once daily on Days 1–21 of each month for a maximum of 12 months

### **Dosing Schedule for Patients with Relapsed or Refractory DLBCL**

#### **Rituximab**

#### Dose-Escalation Phase, Induction

Patients will receive rituximab 375 mg/m^2 IV on Day 1 of each 28-day cycle for up to 6 cycles.

#### Expansion Phase, Induction

Patients will receive rituximab 375 mg/m^2 IV on Day 1 of every other month (i.e., every 2 months) starting with Month 1 (i.e., Months 1, 3, 5) for up to 6 cycles.

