### **3.1.3.2 DLBCL Expansion Phase**

*The expansion phase is designed to further assess the safety and efficacy of lenalidomide when combined with a fixed dose of rituximab and polatuzumab vedotin in DLBCL patients.*

*Approximately 40 patients with DLBCL will be enrolled during the expansion phase and treated as described below.*

All patients enrolled in the expansion phase will receive induction treatment as outlined in [Table 9](#). When study treatments are given on the same day, they will be administered sequentially in the following order: lenalidomide, rituximab, and polatuzumab vedotin.

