**Table 10 Post-Induction Treatment for the DLBCL Expansion Phase**

Patient Population	Regimen
Patients with DLBCL	
Consolidation treatment consisting of the following, administered for approximately 6 months (Months 1–6):
 
 
• Lenalidomide 10 mg PO once daily on Days 1–21 of each month, for a maximum of 6 months
 
• Rituximab 375mg/m^2 IV on Day 1 of every other month (i.e., every 2 months) starting with Month 1 (i.e., Months 1, 3, 5)
 

DLBCL = diffuse large B-cell lymphoma; IV = intravenous; PO = by mouth.

Notes: A month is defined as 28 days. Treatments will be administered sequentially in the following order: lenalidomide followed by rituximab.

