### **4.3.2.2 Rituximab**

*Rituximab will be administered by IV infusion at the dose of 375 mg/m^2 on Day 1 of Cycles 1–6 during induction treatment and on Day 1 of every other month (i.e., every 2 months) during consolidation treatment for patients with R/R DLBCL.*

*Body surface area (BSA) will be determined at screening and should be used to calculate the dose of rituximab throughout the study unless the patient's weight increases or decreases by >10% from screening, in which case BSA should be recalculated and used for subsequent dosing. In obese patients (defined as body mass index  $\geq 30$  kg/m^2), there is no BSA cap and actual body weight, not adjusted weight, is recommended. Empiric dose adjustment for obese patients may be implemented per institutional guidelines.*

*The infusion of rituximab may be split over 2 days if the patient is at increased risk for an IRR (high tumor burden or high peripheral lymphocyte count). Administration of rituximab may be continued on the following day, if needed, for patients who experience an adverse event during the rituximab infusion.*

*If a dose of rituximab is split over 2 days, both infusions must occur with appropriate premedication (see Section 4.3.2.5) and at the first infusion rate (see Table 12).*

*Rituximab infusions will be administered according to the instructions in Table 12. During the treatment period, rituximab must be administered to patients in a setting where full emergency resuscitation facilities are immediately available. Patients should be under close supervision of the investigator at all times.*

*Rituximab should be administered as a slow IV infusion through a dedicated line. After the end of the first infusion, the IV line or central venous catheter should remain in place for  $\geq 2$  hours in order to administer IV drugs, if necessary. If no adverse events occur after 2 hours, the IV line may be removed or the central venous catheter may be de-accessed. For subsequent infusions, the IV line or central venous catheter should remain in place for at least 1 hour after the end of the infusion. If no adverse events occur after 1 hour, the IV line may be removed or the central venous catheter may be de-accessed.*

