- hh For patients with bone marrow involvement at screening, a repeat assessment will be performed at EOI if there is radiologic evidence of a complete response, and during consolidation or at EOC if there is radiologic evidence of a complete response or if clinically indicated (e.g., if there is clinical suspicion of progressive disease in the bone marrow with no radiologic evidence of progression).
- ii Refer to Section 4.3.2 for details on dosing and schedule. At each cycle, each patient will be supplied with only enough lenalidomide for that cycle. During consolidation treatment, lenalidomide will be administered for a maximum of 6 months.
- jj *If PET-CT scan is positive at EOI, perform repeat PET-CT at EOC.*

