### Pharmacokinetic and Immunogenicity Sampling Schedule for Rituximab, Polatuzumab Vedotin, and Lenalidomide in Relapsed or Refractory DLBCL Patients (cont.)

Study Visit		Serum Rituximab PK Sample a,b	Serum Polatuzumab Vedotin PK Sample for Total Antibody a,b	Plasma Polatuzumab Vedotin PK Sample for Antibody Conjugated MMAE and Unconjugated MMAE a	Plasma Lenalidomide PK Sample a	Serum Rituximab HACA Sample a	Serum Polatuzumab Vedotin ATA Sample a
Cycle 2	Day 1	Pre-infusion (within 5 hr prior to dose); 30 ± 10 min after end of infusion	Pre-infusion (within 5 hr prior to dose)	Pre-infusion (within 5 hr prior to dose); 30 ± 10 min after end of infusion	-	Pre-infusion (within 5 hr prior to dose)	Pre-infusion (within 5 hr prior to dose)
Cycle 4	Day 1	Pre-infusion (within 5 hr prior to dose); 30 ± 10 min after end of infusion	Pre-infusion (within 5 hr prior to dose)	Pre-infusion (within 5 hr prior to dose); 30 ± 10 min after end of infusion	-	Pre-infusion (within 5 hr prior to dose)	Pre-infusion (within 5 hr prior to dose)
Cycle 6 (End of Induction)	Day 1	Pre-infusion (within 5 hr prior to dose); 30 ± 10 min after end of infusion	-	Pre-infusion (within 5 hr prior to dose)	2 hr post-dose (± 10 min) c	Pre-infusion (within 5 hr prior to dose)	-
Consolidation Phase (Post-Induction – DLBCL Patients; 28-Day Cycles)							
Treatment discontinuation	-	-	Anytime during visit	-	-	Anytime during visit	Anytime during visit
120 days after last dose	-	-	Anytime during visit	-	-	Anytime during visit	Anytime during visit
1–2 years after last dose	-	-	Anytime during visit	-	-	Anytime during visit	Anytime during visit

## Appendix 4

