### *Pharmacokinetic and Immunogenicity Sampling Schedule for Rituximab, Polatuzumab Vedotin, and Lenalidomide in Relapsed or Refractory DLBCL Patients (cont.)*

Study Visit	Serum Rituximab PK Sample a,b	Serum Polatuzumab Vedotin PK Sample for Total Antibody a,b	Plasma Polatuzumab Vedotin PK Sample for Antibody Conjugated MMAE and Unconjugated MMAE a	Plasma Lenalidomide PK Sample a	Serum Rituximab HACA Sample a	Serum Polatuzumab Vedotin ATA Sample a
--------------------	---	--	---	---	---	--

ATA =anti-therapeutic antibody; HACA =human anti-chimeric antibody; " - " =not applicable; PK =pharmacokinetic.

a Sample collection timing is relative to specified drug.

b Samples collected for PK, HACA, and ATA analysis may be used for additional PK, HACA, and ATA assay development and validation and additional immunogenicity characterization, at the discretion of the clinical pharmacologist and/or the clinical scientist.

c On lenalidomide PK sampling visits, lenalidomide dose will be taken at the clinic appointment.

d If the Cycle 1 Day 1 dose of rituximab is split over two days, take the 30 minutes post-end of infusion rituximab PK sample relative to the end of the infusion on Day 2 and ensure that the date and time of the PK collection are accurately recorded.

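### The synopsis halves rituximab in DLBCL expansion induction (3 infusions against 6 in Section 4.3.2.2), and Table 9 lists the escalation lenalidomide doses instead of the RP2D

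*Combined protocol and SAP*

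**What the plan says.** **Rituximab, DLBCL expansion induction.** The synopsis dosing schedule gives 375 mg/m² on Day 1 of "every other month (i.e., every 2 months) starting with Month 1 (i.e., Months 1, 3, 5) for up to 6 cycles". The entry just above it, for dose-escalation induction, reads "IV on Day 1 of each 28-day cycle for up to 6 cycles". Section 4.3.2.2, which does not distinguish the two phases, gives rituximab "on Day 1 of Cycles 1–6 during induction treatment". Table 9 has a single row for Cycles 1–6 with rituximab on Day 1. Appendix 2 marks rituximab on Day 1 of Cycle 1 and of Cycles 2–6, with a footnote: "Refer to Section 4.3.2 for details on dosing and schedule".

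**Lenalidomide, DLBCL expansion induction.** Section 3.1.3.2 states "All patients enrolled in the expansion phase will receive induction treatment as outlined in" Table 9. The lenalidomide line there offers 10, 15 or 20 mg and is identical to the line in Table 6 for dose escalation. The synopsis entry for the DLBCL expansion and Sections 3.3.3.3, 4.2 and 4.3.2.4 all say RP2D. Table 4, the FL counterpart of Table 9, also says RP2D.

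**Polatuzumab vedotin, FL expansion induction.** The synopsis gives the RP2D in mg by the oral route. Table 4 gives mg/kg intravenously, and Section 4.3.2.3 describes intravenous infusion.

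**The concern.** These are dosing instructions in the current text, not superseded wording from the amendment summary, and they contradict the operative sections. I found no statement that the body overrides the synopsis.

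The rituximab conflict falls entirely within the six cycles before the primary endpoint, IRC-assessed PET-CT CR at end of induction, is measured. Section 6.6 also pools escalation patients treated at the RP2D with expansion patients by histology. If some sites followed the synopsis, the pooled DLBCL estimate would mix patients planned for 6 infusions with patients planned for 3.

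The lenalidomide conflict is about safety. Table 9 does not restrict expansion patients to the RP2D. If escalation stopped because a dose was not tolerated, Table 9 would still list that dose.

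**Working it through.** **Step 1: reproduce the body's figure.** Section 4.3.2.2 and Table 9 give Day 1 of Cycles 1, 2, 3, 4, 5 and 6, which is 6 infusions. Cumulative dose: 6 × 375 = 2250 mg/m².

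**Step 2: count the synopsis schedule.** The notes to Table 10 define a month as 28 days, so a month equals an induction cycle and Months 1, 3 and 5 are Cycles 1, 3 and 5. That is 3 infusions: 3 × 375 = 1125 mg/m². The upper limit of six cycles does not change this, because the listed months fix the count.

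**Step 3: compare.** 1125 / 2250 = 0.50, or half the planned induction rituximab.

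**Step 4: likely source.** Table 10, for consolidation, reads "every other month (i.e., every 2 months) starting with Month 1 (i.e., Months 1, 3, 5". The synopsis post-induction entry lists the same months. The expansion induction line has the consolidation schedule with a cycle limit attached.

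**Step 5: cross-check against PK sampling.** For the expansion phase, Appendix 4 schedules rituximab samples on Day 1 of Cycles 1, 2, 4 and 6. For Cycles 2, 4 and 6 the entry is "Pre-infusion (within 5 hr prior to dose); 30 ± 10 min after end of infusion"; Cycle 1 also has a pre-infusion and an end-of-infusion sample. Footnote a states "Sample collection timing is relative to specified drug". In total there are 4 visits × 2 samples = 8 samples. On Months 1, 3 and 5 there is no rituximab infusion in Cycles 2, 4 or 6, so 3 of the 4 visits and 3 × 2 = 6 of the 8 samples have no infusion to be timed against. The sampling plan therefore presupposes dosing in the cycles that the synopsis skips.

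**Step 6: lenalidomide.** The RP2D is not known from the documents, so I take each possible value as an assumption:

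| Assumed RP2D | Higher doses listed in Table 9 | Ratio to RP2D |
|---|---|---|
| 10 mg | 15 and 20 mg | 1.5 and 2.0 |
| 15 mg | 20 mg | 20/15 = 1.33 |
| 20 mg | none | – |

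Section 4.3.2.4 also mentions de-escalation to 5 mg. If that became the RP2D, all three listed doses would exceed it (10/5 = 2, 15/5 = 3, 20/5 = 4) and the RP2D itself would be missing from the table.

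**Step 7: polatuzumab.** No arithmetic applies. Section 4.3.1.3 describes a sterile lyophilisate and Section 4.3.2.3 its reconstitution for infusion, so the oral instruction cannot be carried out.

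**The case against.** The strongest reply is that nobody would be misled for long. The rituximab error sits in one synopsis line, while Section 4.3.2 refers readers to the regimen tables. A site dosing from the synopsis would meet the conflict on Day 1 of Cycle 2, when Table 9 and Appendix 2 call for rituximab and Appendix 4 asks for a sample after its infusion. Losing half the planned dose therefore requires ignoring several sections for six cycles, and quoting it against the whole cohort is a worst case. That is fair as to likelihood. It does not remove the contradiction.

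On lenalidomide, Table 9 can be read as listing candidate values, and the RP2D rule appears in several other places. The RP2D goes to the Internal Monitoring Committee for approval before the DLBCL expansion opens (Section 3.1.3.1), the Sponsor approves each enrollment (Section 4.2), and outside the United States lenalidomide is dispensed through the IxRS (Section 4.3.3). These controls lower the lenalidomide risk. They do not address the rituximab schedule: the Section 4.2 approval concerns eligibility. Nor do they change the fact that the table to which sites are sent omits the restriction.

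Two further points stand. The polatuzumab slip is purely typographical and adds no risk. And because Section 3.1.3.1 allows altered lenalidomide schedules and polatuzumab de-escalation if the MTD is exceeded, replacing only the lenalidomide dose in Table 9 may not be enough.

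**Conclusion.** The concern holds and should be fixed. For DLBCL expansion induction, the synopsis prescribes 3 rituximab infusions (1125 mg/m²) where the body prescribes 6 (2250 mg/m²), a 50% shortfall for any patient dosed from that line throughout; about 40 patients are planned. Table 9 fails to limit lenalidomide to the RP2D, and how much that matters depends on an RP2D not yet determined: nothing listed exceeds it at 20 mg, while the highest listed dose is 1.33 times the RP2D at 15 mg and twice the RP2D at 10 mg.

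This is an internal inconsistency with a clear intended answer. The sample size, confidence intervals and decision rules do not change. The conclusion rests on the plan's 28-day month and on reading Months 1, 3 and 5 literally.

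**What to change.** Make three corrections:

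1. **Synopsis, DLBCL rituximab, expansion induction:** replace the every-other-month schedule with that of the dose-escalation entry, "IV on Day 1 of each 28-day cycle for up to 6 cycles", at 375 mg/m².
2. **Table 9:** replace the three lenalidomide doses with the DLBCL RP2D, following the form of Table 4. Keep Days 1–21 unless escalation leads to a different schedule. If the polatuzumab dose is reduced under Section 3.1.3.1, update that line as well.
3. **Synopsis, FL polatuzumab vedotin, expansion induction:** change the unit to mg/kg and the route to intravenous.

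The cost is three one-line edits in the next amendment, or a clarification letter to sites. The schedule of assessments and the analysis stay as they are.
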